4.1.1 OA TREATMENT ALGORITHM

LOR Injections:

- On Day 1, after subject eligibility has been confirmed and subjects complete all PRO measurements and functional tests (at applicable sites), subjects will receive an IA injection of 0.07 mg LOR into one or both knees. Bilateral injections of 0.07 mg LOR are allowed.
- Subjects may receive additional injections of LOR into one or both knees, as clinically indicated, at any time between Day 1 and Month 33 with the restriction that LOR injections into the same knee must be separated by at least 6 months; these injections can occur at Unscheduled Injection Visits, 3-Month Post-Injection Follow-Up Visits, or at the Months 3, 12, or 24 visits after the completion of visit assessments.
- *For LOR injections after Day 1:* Within 6 months of any knee surgery, LOR may not be injected in the affected knee without consultation with and documented approval from the Medical Monitor.

Glucocorticoid and HA Injections:

- Between Day 1 and Month 3, subjects are prohibited from receiving any injections other than LOR into either knee.
- Subjects may receive injections of glucocorticoid or HA into one or both knees, as clinically indicated, at any time between Month 3 and Month 33 with the restriction that glucocorticoid and HA injections must be performed in accordance with US prescribing information (USPI); these injections can occur at Unscheduled Injection Visits, 3-Month Post-Injection Follow-Up Visits, or at the Months 3, 12, or 24 visits after the completion of visit assessments.
 - For subjects who receive HA as a series of injections, the first injection can occur at an Unscheduled Injection Visit, 3-Month Post-Injection Follow-Up Visit, or at the Months 3, 12, or 24 visits after the completion of visit assessments. The subsequent injections in the series should be entered into the database as Unscheduled Visits (PRO measurements and functional tests do not need to be performed at these visits).

General Injection Guidelines:

- If receiving an injection for the indication of OA, subjects may only be injected in the knee(s) for which OA diagnosis has been confirmed based on ACR criteria ([Appendix 1](#)). If one of the subject's knees did not fulfill ACR criteria at Screening, knee OA based on

these criteria must be confirmed in that knee prior to the first injection at any time in the study.

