5.3 LIFESTYLE GUIDELINES

5.3.1 CONTRACEPTION

WOMEN OF CHILDBEARING POTENTIAL

Women of childbearing potential (WOCBP) refers to women who are not post-menopausal (defined as 12 months with no menses without an alternative medical cause) or permanently surgically sterile (includes hysterectomy, bilateral salpingectomy, and bilateral oophorectomy).

From the Screening Visit until Month 36 (EOS)/ET, sexually active WOCBP must agree to use an acceptable form of contraception. Acceptable forms of contraception are:

1. Intrauterine device (IUD)
2. Implantable rod
3. Established hormonal contraceptive methods. This includes combined (estrogen and progestogen containing) hormonal contraception associated with inhibition of ovulation (oral, intravaginal, or transdermal); progestogen only hormonal contraception associated with inhibition of ovulation (oral, injectable, or implantable). Females who are using hormonal contraceptives must have had consistent use of the same hormonal contraceptive product for at least 4 weeks.
4. Bilateral tubal ligation/occlusion/division

5. Male partner who had a vasectomy provided that the partner is the sole sexual partner of the WOCBP, and that the vasectomized partner has received medical assessment of the success of the surgical procedure or had the vasectomy for at least 6 months

Sexually active WOCBP who withdraw from the study after receiving study medication should remain on an acceptable form of contraception for 1 month after their last LOR injection.

MEN

For men, no contraception measures are required.

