6.1.9 DURATION OF THERAPY

LOR is to be administered as an IA injection into one or both knee joints once at Day 1. Subjects may have unscheduled visits at any time for additional injections of LOR (between Day 1 and Month 33) or glucocorticoid or HA (between Month 3 and Month 33) into either knee as clinically indicated, with the restrictions that 1) LOR injections into the same knee must be separated by at least 6 months, and 2) glucocorticoid and HA injections must be performed in accordance with their USPIs. The subject should not have any condition that, in the opinion of the Investigator, constitutes a risk or contraindication for the injection.

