7.2.2 OTHER ASSAYS OR PROCEDURES

Pregnancy Test

A serum-based pregnancy test will be performed on WOCBP at the Screening Visit and a urine-based pregnancy test will be performed on WOCBP at Day 1 and Month 36 (EOS)/ET. Results from the Screening Visit and Day 1 pregnancy tests will be utilized to determine subject eligibility.

WOCBP are women who are not post-menopausal (defined as 12 months with no menses without an alternative medical cause) or permanently surgically sterile (includes hysterectomy, bilateral salpingectomy, and bilateral oophorectomy).

Drug Test

A urine sample for drug testing will be collected at the Screening Visit. The urine drug test will identify amphetamine, buprenorphine, cocaine, methadone, opiates, PCP, propoxyphene, barbiturates, and benzodiazepine. Results from the drug test will be utilized to determine subject eligibility.

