- ^d If possible, the ET visit should be performed within 14 days of subject premature withdrawal or termination. PRO measurements (WOMAC, KOOS, pain NRS, SF-12, PASS, WPAI) and functional tests (40-meter walk test and TUG test) do not need to be completed at the ET visit if they were completed within 2 weeks prior.
- ^e Review medical history to capture End Date(s), if applicable, of any ongoing medical history(ies) collected at the Screening Visit.
- ^f A serum pregnancy test will be performed on WOCBP at the Screening visit and a urine pregnancy test will be performed on WOCBP at Day 1 and Month 36 (EOS)/ET.
- ^g At Unscheduled Injection Visits, 3-Month Post-Injection Follow-Up Visits, or at Months 3, 12, or 24 (after completion of all visit assessments), subjects may receive LOR, glucocorticoid, or HA in either knee. Refer to the OA Treatment Algorithm in [Section 4.1.1](#) for further details.
- ^h Subjects are to receive an IA injection of LOR into one or both knees on Day 1.
- ⁱ Functional tests will only be performed at a subset of sites.
- ^j For any subjects who have a total or partial knee replacement of the knee diagnosed with OA in unilateral OA or of either knee in bilateral OA, sites should follow up with these subjects approximately 6 months after the total or partial knee replacement surgery is completed to assess outcomes of the surgery.

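### Tested pregnancy status is a condition of the first lorecivivint injection, but no test is required before any repeat injection and the protocol does not say why

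*Protocol*

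**What the plan says.** **First dose.** Exclusion 1 (Protocol 5.2) bars pregnant women, and WOCBP whose test is positive or indeterminate. Section 7.3.1 puts a serum test at Screening, no more than 14 days before Day 1. Section 7.3.2 adds a urine test on Day 1, before enrollment. Section 7.2.2 says that both results decide eligibility.

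**Later tests.** Section 7.2.2 states that "a urine-based pregnancy test will be performed on WOCBP at Day 1 and Month 36 (EOS)/ET". Footnote f to the Schedule of Events (7.3.7) agrees: "a urine pregnancy test will be performed on WOCBP at Day 1 and Month 36 (EOS)/ET".

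**Later doses.** On Day 1, "subjects will receive an IA injection of 0.07 mg LOR into one or both knees". Further LOR may be given "as clinically indicated, at any time between Day 1 and Month 33" (4.1.1), and 6.1.9 repeats that window. The only spacing rule is that "LOR injections into the same knee must be separated by at least 6 months". Re-injection may take place at Month 3 (in the knee not treated on Day 1), at Months 12 and 24, at Unscheduled Injection Visits and at 3-Month Post-Injection Follow-Up Visits. None of the procedure lists for these visits in 7.3.3 and 7.3.4 contains a pregnancy test, nor does the laboratory panel in 7.2.1.

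**Other safeguards.** Section 5.3.1 requires sexually active WOCBP to agree to contraception from Screening to Month 36/ET. Section 4.1.1 asks the Investigator to judge suitability before each injection. Section 5.6.1 lists pregnancy as a possible reason for discontinuation, and 8.4.5 requires any pregnancy to be followed to its outcome.

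**The concern.** The protocol sets its own standard for the first dose and does not carry it forward. At entry it does not rely on a serum result up to 14 days old but repeats the test on the day of injection. For later injections of the same drug, whose dose may not be modified (6.1.8), the most recent required result can be as much as 33 months old. Nothing in the protocol explains the difference.

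The protocol also treats reproductive precaution as relevant to more than the first dose. WOCBP who withdraw after treatment "should remain on an acceptable form of contraception for 1 month after their last LOR injection" (5.3.1), which ties that period to the latest injection.

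At stake is a repeat injection given during an unrecognised pregnancy, with no scheduled step to detect the pregnancy beforehand.

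**Working it through.** The documents state no maximum number of LOR visits, so there is no planned figure to reproduce. The check has two parts: counting the permitted repeat visits, and comparing the safeguards at each dose.

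**1. Permitted LOR visits after Day 1**

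Inputs, all from Protocol 4.1.1 and 7.3.3:

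- LOR window: Day 1 to Month 33
- Minimum interval: 6 months within the same knee, with no minimum between knees
- Day 1: one or both knees
- Second knee: may start after Day 1, for example at Month 3

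Formulas:

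- Knee dosed on Day 1: further injections = floor(33/6) = 5 (Months 6, 12, 18, 24, 30).
- Knee first dosed at Month *b* after Day 1: injections = 1 + floor((33 − *b*)/6). For *b* = 3 this is 1 + floor(30/6) = 6 (Months 3, 9, 15, 21, 27, 33). For *b* = 4 it is 1 + floor(29/6) = 5.
- Both knees dosed on Day 1, second knee then delayed to Month 7: 1 + floor(26/6) = 5 for that knee.

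| Pattern of use | Maximum further LOR visits |
|---|---|
| One knee only | 5 |
| Both knees, always on the same day | 5 |
| Both knees on Day 1, staggered afterwards | 5 + 5 = 10 |
| One knee on Day 1, other started at Month 4 | 5 + 5 = 10 |
| One knee on Day 1, other started by about Month 3 | 5 + 6 = 11 |

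Sensitivity to the day convention: the count was repeated with 6 months taken as 180, 182, 183 or 184 days, and Month 33 as Day 990 or Day 1004. The maximum was 11 every time. The latest start for the second knee that still gives 11 ranged from Day 70 (70 + 5 × 184 = 990) to Day 104 (104 + 5 × 180 = 1004).

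**2. Timing of the Month 36 test**

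The protocol counts months as 30 days (Month 36 = Day 1080), so Month 33 is Day 990. The Month 36 window is ±28 days, so the earliest date is Day 1080 − 28 = Day 1052, which is 1052 − 990 = 62 days after a Day 990 injection. Nominally the gap is 1080 − 990 = 90 days. An ET test can come sooner. In each case the test follows the last dose and cannot inform it.

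**3. Safeguards at first and repeat dose**

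| Safeguard | Day 1 injection | Repeat LOR injection |
|---|---|---|
| Pregnancy test result required | Yes: serum at Screening and urine on Day 1 | No |
| Contraception, sexually active WOCBP | Yes | Yes |
| Investigator's suitability judgement | Yes | Yes, no test named |

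Only the first row differs.

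**The case against.** The best defence is that the passages agree with one another. Sections 7.2.2, 7.3.2, 7.3.5, 7.3.6 and the Schedule of Events all give the same test times. Section 7.2.2 presents the early tests as eligibility tests, and exclusion 1 is an entry criterion. A reader might infer that the protocol contradicts itself. It does not: an entry test that is not repeated is an omission or an unstated choice. This objection stands.

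The contraception rule is also stronger than the sentence about women who withdraw suggests. It runs from Screening to Month 36/ET whatever the injection dates, its accepted methods do not include barrier methods, and unwillingness to comply is itself an exclusion. Nothing stops an Investigator from testing before a repeat dose. So a reader should not take it that repeat doses would go untested, only that no test is required. This stands too, but a contraception rule and a clinical judgement are not a test result, and the protocol did not treat them as enough on Day 1.

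Eleven visits is an extreme. It needs confirmed OA in both knees, a one-knee Day 1 injection, an early start in the other knee, and minimum-interval dosing throughout. A reader might take it as typical use; the documents give no reason to.

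A reader might also infer known fetal harm, or damage to the primary safety data. The protocol and SAP report no reproductive risk for LOR and refer to the Investigator's Brochure, which is not available here. The safety endpoints are adverse events, laboratory measures and vital signs, and nothing in the documents puts a size on any effect on them.

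Finally, SAP section 4 (Overall Study Design and Plan) says that the sponsor stopped the study early, and SAP 8.2 says that no subject completed a post-baseline laboratory visit, first scheduled at Month 12. If that means no dosing at or after Month 12, the same spacing rule leaves at most 3 repeat LOR visits (Month 6 in one knee, Months 3 and 9 in the other). That limits what happened. It does not rule out some re-injection, and it does not alter the 36-month plan.

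**Conclusion.** The point holds as an unexplained inconsistency between the conditions for the first and later LOR doses. A WOCBP could have up to 5 further LOR visits under one-knee or same-day bilateral use, and at most 11 under the most intensive staggered use, with no pregnancy test required before any of them. The oldest result still in force could be 33 months old at the last permitted dose, against same-day testing at the first.

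These counts are ceilings set by the protocol text, not expected use; a subject who is never re-injected contributes none. They assume dosing at the minimum interval up to Month 33. The number of WOCBP in the 40 to 80 age range is not stated, so the number of women affected cannot be estimated. The importance of the gap depends on reproductive information that these documents do not contain, and actual exposure was cut short by termination.

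**What to change.** The sponsor should reconcile footnote f, section 7.2.2 and the injection-visit procedure lists in 7.3.3 and 7.3.4 with exclusion 1 and section 4.1.1. After that, either the pregnancy-status condition for repeat LOR injections is consistent with the one for Day 1, or the protocol states why it differs. Which of the two is a clinical decision for the sponsor, and no testing rule is proposed here.

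If the sponsor justifies the difference, the cost is a sentence or two in 4.1.1. If it aligns the conditions, the cost is at most a schedule entry, a few extra urine kits of a type already in use, and some minutes for WOCBP at visits already taking place. Since this study has ended, the change matters mainly for any later protocol that reuses this schedule.

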7.4 JUSTIFICATION FOR SENSITIVE PROCEDURES

Not applicable for this study.

7.5 CONCOMITANT MEDICATIONS, TREATMENTS, AND PROCEDURES

Details regarding the name, indication, route of administration, dose, and frequency of all medications taken within 30 days prior to the Screening Visit through Month 36 (EOS)/ET will be recorded in the “Prior and Concomitant Medications” eCRF. “All medications” should include prescription, over-the-counter, supplements, and herbal or alternative medications, as well as glucocorticoid and HA injections for indications other than OA.

Procedures or non-drug therapies that are ongoing, new, or modified at or after the Screening Visits must be recorded on the “Procedures and Non-Drug Therapies” eCRF.

AE assessments should include consideration of any new or modified concomitant therapies administered to the subject.

7.5.1 PRECAUTIONARY MEDICATIONS, TREATMENTS, AND PROCEDURES

Not applicable to this study.

7.6 PROHIBITED MEDICATIONS, TREATMENTS, AND PROCEDURES

Prohibited Concomitant Medications and Procedures:

- Any IA injection other than LOR, glucocorticoids, and HA including PRP, stem cell therapies, or other agents with therapeutic intent, into either knee is prohibited while the subject is on study; IA injection of glucocorticoids, HA derivatives, PRP, stem cells, or other therapeutic agents into joints other than the knee is allowed.
- Drugs screened to assess eligibility (i.e., amphetamine, buprenorphine, cocaine, methadone, opiates, PCP, propoxyphene, barbiturates, and benzodiazepine) are prohibited while the subject is on study unless prescribed by a physician to treat a specific condition.
- Subjects are prohibited from participating in any other clinical research trial that includes the receipt of an IP or any experimental therapeutic procedure.

The Investigator should notify the Sponsor Medical Monitor if any prohibited therapies are required to ensure subject safety.

7.7 PROPHYLACTIC MEDICATIONS, TREATMENTS, AND PROCEDURES

Not applicable to this study.

7.8 RESCUE MEDICATIONS, TREATMENTS, AND PROCEDURES

Not applicable to this study.

7.9 PARTICIPANT ACCESS TO STUDY AGENT AT STUDY CLOSURE

Not applicable to this study.

8. ASSESSMENT OF SAFETY

8.1 SPECIFICATION OF SAFETY PARAMETERS

Safety assessments include physical examinations, vital signs, clinical laboratory tests, collection of AEs and concomitant medications, and general medical evaluations.

8.1.1 DEFINITION OF ADVERSE EVENTS (AE)

AEs in the eCRF will be classified according to the most recent US FDA definitions and in a manner consistent with ICH-GCP guidelines. As such the following definitions will be used:

An AE is any unfavorable and unintended sign, symptom, or disease temporally associated with the use of an IP or other protocol-imposed intervention, regardless of attribution. An AE may include intercurrent illnesses or injuries that represent an exacerbation (increase in frequency, severity, or specificity) of preexisting conditions (e.g., worsening of asthma).

Whenever possible, it is preferable to record a diagnosis as the AE term rather than a series of symptoms relating to a diagnosis. Fluctuations of pre-existing conditions, including the disease under study that does not represent a clinically significant exacerbation or worsening, need not be considered AEs. In order to classify AEs and diseases, preferred terms will be assigned by the Sponsor to the original terms entered on the eCRF, using the Medical Dictionary for Regulatory Activities (MedDRA).

In this protocol, signs and symptoms of exacerbation or worsening of knee OA will be captured in the context of efficacy assessments and recorded on specific pages of the eCRF. Anticipated fluctuations or anticipated deterioration (in the opinion of the Investigator) of the underlying disease (knee OA) will not be considered as AEs nor captured on the AE page of the eCRF.

8.1.2 DEFINITION OF SERIOUS ADVERSE EVENTS (SAE)

An SAE is an AE that meets one or more of the following criteria:

- Results in death
- Is life threatening
- Requires inpatient hospitalization or prolongation of existing hospitalization
- Results in persistent or significant disability/incapacity
- Is a congenital anomaly/birth defect
- Is an important medical event, defined as an event that does not fit one of the other outcomes, but may jeopardize the subject and may require medical or surgical intervention (treatment) to prevent one of the other outcomes. Examples include allergic bronchospasm (a serious problem with breathing) requiring treatment in an emergency room (ER), serious blood dyscrasias (blood disorders), or seizure/convulsion that does not result in hospitalization. The development of drug dependence or drug abuse would be other examples of important medical events.

The term "life-threatening" in the definition of "serious" refers to an event in which the subject was at risk of death at the time of the event; it does not refer to an event that hypothetically might have caused death if it were more severe.

“Inpatient hospitalization” is clarified as hospitalization lasting ≥ 24 hours. Admission to the hospital or prolongation of hospitalization qualifies as an SAE only if it is the result of an AE.

All SAE information must be recorded on the SAE form approved by the Sponsor. Additional follow-up information (e.g., test results, autopsy, and discharge summary) may be requested to supplement the SAE report form and can be attached as de-identified records.

8.1.3 DEFINITION OF UNANTICIPATED PROBLEMS (UP)

An AE observed during the conduct of a study should be considered an Unanticipated Problem (UP) involving risk to human subjects, and be reported to the IRB, only if it was unexpected, serious, and would have implications for the conduct of the study (e.g., requiring a significant, and usually safety-related, change in the protocol, such as revising inclusion/exclusion criteria or including a new monitoring requirement, informed consent, or IB). The occurrence of such an event would suggest that the research places study participants or others at a greater risk of harm.

FDA recommends that there be careful consideration of whether an AE is a UP that must be reported to IRBs. In summary, FDA believes that only the following AEs should be considered as UPs that must be reported to the IRB:

- A single occurrence of a serious, unexpected event that is uncommon and strongly associated with drug exposure (such as angioedema, agranulocytosis, hepatic injury, or Stevens-Johnson syndrome)
- A single occurrence, or more often a small number of occurrences, of a serious, unexpected event that is not commonly associated with drug exposure, but uncommon in the study population (e.g., tendon rupture, progressive multifocal leukoencephalopathy)
- An AE that is described or addressed in the IB, protocol, or informed consent documents, but occurs at a specificity or severity that is inconsistent with prior observations
- An SAE that is described or addressed in the IB, protocol, or informed consent documents, but for which the rate of occurrence in the study represents a clinically significant increase in the expected rate of occurrence (ordinarily, reporting would only be triggered if there were a credible baseline rate for comparison)
- Any other AE or safety finding (e.g., based on animal or epidemiologic data) that would cause the sponsor to modify the IB, study protocol, or informed consent documents, or would prompt other action by the IRB to ensure the protection of human subjects

8.2 CLASSIFICATION OF AN ADVERSE EVENT

8.2.1 SEVERITY OF EVENT

The Investigator will assess AEs for severity utilizing the CDISC AESEV, which classifies AEs as mild, moderate, or severe ([Table 1](#)).

Table 1: CDISC Definitions of Adverse Event Severity

CDISC Submission Value	CDISC Definition
MILD	A type of adverse event that is usually transient and may require only minimal treatment or therapeutic intervention. The event does not generally interfere with usual activities of daily living.
MODERATE	A type of adverse event that is usually alleviated with additional specific therapeutic intervention. The event interferes with usual activities of daily living, causing discomfort but poses no significant or permanent risk of harm to the research participant.
SEVERE	A type of adverse event that interrupts usual activities of daily living, or significantly affects clinical status, or may require intensive therapeutic intervention.

